### Week 1 Practice:

How does the **threat** system get in the way of your sex life?

Acknowledging these difficulties and the emotions such as anger/shame that come along with them is the first step in building the soothing system to allow yourself to let go of some of these difficult feelings.

## Session 2 – Being in the present moment and Grounding techniques

### Script

Hello and welcome to the second session. Today's session focuses on being in the present moment. These days we are so busy multitasking and doing many things that we may not be living our lives fully present. Additionally, we also know that the experience of trauma can make it even harder to be present because our minds may be elsewhere thinking about past events and at times, you may get involuntarily pulled into flashbacks or trauma memories without wanting to experience these memories.

In this session, we will learn about being present also known as mindfulness and learning about grounding techniques. As with each week, the core of these sessions is to build compassion towards the way our minds and bodies behave. We will practice some mindfulness exercises and I invite you to participate in whatever way feels right for you. With each exercise, you can choose if you want to try it and even if you choose not to, that's okay. You have showed up today and that can be enough.

#### Mindfulness - Living Everyday on Autopilot

We do many things every day without thinking or being aware of what we are doing. Think about times you are travel between two places and don't really remember the journey. Still, before you know it, you've arrived at your destination. **We call this autopilot mode.** In many ways, it can help us – routine tasks can be done easily, without thought. However, it also means we do many things without much awareness of what is happening and fail to be fully present and get the most from the experience. Living in autopilot also means our minds are less focused on what we are doing, and instead, it may be elsewhere. If you've had an experience of sexual assault, your mind may wander onto things associated with that experience even when you are doing something completely different. However, it is also common to think about the past experience of sexual assault when you are intimate with a partner. In the same way a task such as making a cup of tea becomes an automatic habit, so can worrying thoughts, unhelpful behaviours, and difficult feelings become an automatic habit if we are not conscious of being in the present.

Mindfulness offers a way to step out of autopilot and the unhelpful habits that come with it. It can help us get more from our day to day experience – to be more present in the things that we do. But it can also allow us to step back from difficult emotions – to be less caught up in them.

Mindfulness can be described as: awareness of present moment with acceptance. So, what do we mean by this? If we take each of the three phrases underlined above in turn, we can understand this statement better.

Awareness can be broken down into three steps:

#### Stop or slow down

When we are acting in autopilot we respond to situations, thoughts and emotions in automatic ways. The first step towards being more mindful, is to stop or slow down what you were doing – give yourself some space. Giving yourself some space can allow your mind to settle and provides a basis for reacting in a different way.

### Observe

The next step is to observe what is going on for us. To do this, we first focus our attention on something – this can be on anything – e.g. and object around us, sounds that are going on around us. Most commonly, we can focus our attention on our breath. As we do so, we begin to notice the things that take our attention away from our breath. We notice where our attention goes.

### Return

Once we have noticed that we have become distracted, that something has taken our attention away from our breath, we can note what has taken our attention away, and then return our attention back to our breath.

### Present Moment

Sometimes we can be completely absorbed in the activity we are doing. However sometimes many things can take our attention away from our present experience. Mindfulness is a way to bring us back to the present moment.

### Acceptance

The present moment is affected by how we view or judge it. To accept the present is to experience it without judging it. It is to see things in the moment as they are, not as we might want or expect them to be, or what we fear they might become. We are accepting our experience, pleasant or unpleasant, as it is.

### How can mindfulness help after trauma?

Studies have found that mindfulness helps reduce distracting thoughts, increases focus on physical sensation, and is helpful for sexual difficulties. It helps us learn to be in the moment by being aware of our physical sensations. And we want to build on compassion and activate our soothing system which we can do through mindfulness.

However, some survivors of sexual trauma may find mindfulness difficult or triggering and dissociates. Mindfulness may be quite distressing if it means sitting with sensations and emotions that are usually avoided. and If your mind ‘shuts off’ during your experience of trauma, the feeling of ‘shutting off’ can occur again when you’re faced with similar or difficult emotions. If you experience these difficulties, it’s okay. It’s a protective mechanism to keep you safe. You can opt-out of the mindfulness exercise and practice being present in a different way. One way to do this is through everyday mindfulness.

### Everyday Mindfulness

In any task we do, we can be mindful and present. Choose a routine task and each day for the next week; see if you can remember to pay attention while doing it. You do not have to slow it down or even enjoy it. Simply do what you normally do, but see if you can be fully alive to it as you do so.

Examples like: Brushing your teeth. Drinking a hot drink.

We are going to now have a short mindfulness practice – if you know mindfulness is difficult for you because of your experience of sexual trauma, you can skip the practice and I invite you

to do anything you find soothing or if you feel up for it, practice one of the everyday mindfulness activities instead. However, if you would like to give the activity a go, then continue and remember you have control and can stop and move on from this exercise at any point.

To begin, find a comfortable sitting position and if you feel comfortable, closing your eyes.

***Mindfulness Attention Practice – based on Paul Gilbert's exercise. From Compassionate-Mind Guide to Recovering from Trauma and PTSD Deborah A. Lee***

*“Sit quietly for a moment and focus on your breathing. Allow the breath to come down into your diaphragm slowly and evenly and then leave your body slowly and evenly. If you find this difficult you may simply want to try to focus on the sensation of your breath coming in and leaving through your nose. Try spending two minutes simply concentrating on the experience of breathing in and out. If you don’t like focusing on your breathing or you don’t like closing your eyes, you could use a pebble or a shell and try to focus your attention on the experience of looking at it and feeling it or look at a blank wall.*

*As you focus on your in breath and out breath You may notice that within just a few moments your mind will have wandered off on to something else. This is called mind wandering. If there are things that are worrying us, our minds easily get pulled into thinking about them and away from the present moment. This can also happen if there are things we are looking forward to (like a party), or if there are things that we need to do (e.g., pay a bill, or remember to call a friend), and we can find our minds skipping to them. This is very typical of how our minds are, and indeed recent research evidence suggests that it is our natural state.*

*One aspect of practicing mindfulness is just learning to notice when our minds wander and bringing our attention gently and warmly back to what we want to focus on. Mindfulness is not making our minds pay attention or emptying our mind of thoughts. Telling ourselves off for not being able to pay attention is not being mindful either. Indeed, it is counterproductive, as noticing where our minds wander to can be very important in helping us to identify other issues that are bothering us. When our minds wander it is not a sign that we have failed to be mindful; it is a part of the very process of being mindful! It is the act of noticing and then returning the attention to the desired focus that is central to mindfulness. The very fact that you find this difficult is itself evidence that you are engaging in mindful practice!”*

*We are about to draw this mindfulness practice to a close so just focusing on you breathe for a few more moments and then feeling the weight of your body on the chair or floor and when you are ready, bringing yourself back into the room and open your eyes.*

Before we move on I just want you to notice how you feel after that practice, you may feel relaxed, you may feel more tense or you may have noticed how you’re not use to being present and your mind continued to wander. It’s normal if this happens – Mindfulness is like a muscle and the more you practice the easier it gets. If you found the practice difficult as it triggered difficult feelings, you did your best to try out the exercise and should feel proud for being brave to do so. Instead of doing the mindfulness practice in future sessions, you can opt to do whatever you feel comfortable doing.

To finish the session today we will think about managing flashbacks during sex and grounding techniques you can use. Flashbacks are very common in any traumatic experience. And when you are a survivor of sexual trauma, it is common for women to avoid sex because of the associations it brings up and the feelings, sensations and memories sex can trigger. It can be challenging to return to sex even if you are on your own or with a trusted partner. This is not because you chose or want to relive your past but experiencing flashbacks is understandably challenging and scary – it is not your fault that you experience them.

To manage flashbacks during sex, it can be helpful to have a conversation with your partner when you're not having sex. You can discuss why flashbacks occur and that they are not because of anything your partner has done wrong. You can also share or discuss the knowledge you've gained from this intervention with your partner. Remind your partner the confusion is not about them – it's about the situation. We know these conversations can be difficult – we have included a short brief handout (appendix B in your handout sheets) that you could share with your partner if you find it difficult to discuss your traumatic experience and your level of comfort during sex (Appendix B).

During this talk you can discuss with your partner the level of comfort with sex – are there any dos or don'ts specific to you? Anything you would prefer your partner to do/not do? This can start very simple e.g. holding hands, dancing, cuddling up in bed with a film. It can then branch into sexual things you feel comfortable with. We have included a sexual activities list and body map in your handout (Appendix C/D) to introduce the conversation. There is no pressure to do anything you are not comfortable doing, it's okay if this conversation takes time.

If you have been with the same partner prior to experiencing trauma, you may feel bad about having to change the way you have sex but it is not your fault. It may be more uncomfortable having these conversations with a casual partner but it's an important one to have to ensure you feel safe and more confident.

During the discussion, you can plan of action with your partner with the aim to activate your soothing system. The plan can include

- Signal that flashback is occurring (e.g. specific arm pat, or word)
- An Okay to pause and take some time
- Might need to express emotion e.g. cry
- Use grounding technique (next slide)
- As part of grounding - discuss with partner in advance how you would like them to respond in this situation. E.g. you might like partner to say, "it's okay, you are safe with me, I will not hurt you." You might like them to hold you while you feel sad, or for them to sit and listen to how you feel.
- Breathe

This might occur a few times in sex before gradually over time you feel more comfortable and safe. Requires patience and compassion, both self-to-self and other-to-self.

If you have found things that have worked you can use those, these are only some ideas, you might have different ideas

**Grounding Techniques are used to remind you where you are and that you are safe. It can be really helpful to discuss possible grounding techniques you can use with a sexual partner and communicate that with them. It can also be helpful to reflect on what you can use on your own. When thinking of grounding techniques, think about all 5 senses and how you can use your touch, smell, taste, sight and sound. You can write your own ideas below.**

- Grounding object
- Sexual grounding object
- A phrase or object that reminds you WHERE you are and that you are SAFE. E.g. Item of clothing, a particular object (e.g. a stress ball, a ring, a special item) Or a piece of paper with the phrase “you are at your home, you are not in danger, you are safe”.
- Using 5 senses for grounding
  - o Smell: essential oils. Candles
  - o Taste: mint/gum/sour candy
  - o Touch: weighted blanket, furry objects
  - o You can also use the 54321-grounding technique included in your handout. The 54321-grounding technique is simple, yet powerful. Like gradually attaching anchors to the boat, this method slowly pulls you back to earth. It involves you naming 5 things you can see, 4 things you can touch, 3 things you can hear, 2 things you can smell and 1 thing you can taste.

With everything, there is no need to blame or be critical of yourself if you have to make a plan to be intimate and feel safe. Your threat system may activate when you are trying to have sex alone or with a partner because of your experience of trauma and that is not because you want or choose to have sexual distress – it’s how our brains have evolved and are hardwired. It may also be uncomfortable to have these conversations with a partner, and that’s understandable. It may be difficult to find the right words, feelings of shame or guilt, and some people may feel very vulnerable talking about this to anyone. If you experience any of this, it’s not your fault. You have the power to choose when you are ready to have these conversations.

Practicing being present and having a plan should your threat system activate are ways we try to activate the soothe system to help you feel prepared and more confident in returning to sex.

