### Three Systems:

We have already introduced how the threat system can interfere during sex. We also briefly talked about how the soothing system is what makes us feel safe during sex allowing for arousal. These two systems, described above, are part of a three systems model. The third system is the drive system and it's involved in wanting and pursuing sex. From an evolutionary perspective, the principle aim of sex is reproduction. However, we know that is not everybody's drive for sex today.

After experiencing trauma, the threat system becomes more sensitive and is easily triggered, overruling the drive and soothing systems as your brain tries to protect you from being hurt again even if you are with a trusted partner. This may cause people to feel:

- unsafe, scared of sex etc.
- shame about what happened, disgusted with self or others.

- Some people worry that what happened to them was their fault, so might feel shame and feel undeserving of sex or closeness
- Might have critical thoughts like “I’m disgusting” or “I’m not worth it”

Our brains and bodies are not designed to have sex “perfectly” (e.g. in the way our **culture** currently says we should) … we’re evolved to survive...

It is understandable that if someone has had a threatening or unwanted sexual experience, sex might be experienced as threatening. A new sexual encounter might automatically trigger memories of the unwanted sexual experience **OR** sex drive might increase – as the brain’s way of managing the increased threat. This can be **automatic and unconscious**, and happen even if the person doesn’t want it to. The brain is doing what it thinks is helpful, even if it doesn’t feel helpful.

Building Compassion:

Over the next few weeks, we will work on acknowledging the difficulties and shame related to sex while building on the soothing system through different exercises. Increasing our soothing system will help increase our drive and alleviate the threat system. We do this by trying to be more compassionate with ourselves. This includes

- Understanding the way, we are and why we may act/feel this way – being wise about sex and our bodies
- Treating ourselves with warmth and kindness
- Being encouraging to ourselves
- Being non-judgmental about our experiences

Being compassionate will also allow us to be aware and engage with distress and difficulty without turning away from it and increase our motivation and courage to try to alleviate the distress.

Practice:

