## Managing flashbacks during sex

Example actions to include

- Using specific grounding techniques
- A signal to inform your partner that you're having a flashback or want to stop
- Agreeing to pause if things begin to be difficult
- Acknowledging difficult emotions (e.g. fear/anger/disgust/shame)
- Breathing together and engaging soothing system

**Grounding Techniques are used to remind you where you are and that you are safe. It can be really helpful to discuss possible grounding techniques you can use with a sexual partner and communicate that with them. It can also be helpful to reflect on what you can use on your own. When thinking of grounding techniques, think about all 5 senses and how you can use your touch, smell, taste, sight and sound. You can write your own ideas below.**

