## Sensate Focus

If you have a trusted partner who you want to try an exercise with, you can try sensate focus which is practicing intimacy without genital contact. Sensate Focus is a set of exercises geared towards couples where the focus of sex is shifted from pursuing a particular outcome (e.g. penetration or orgasm), to a slower appreciation of physical intimacy and sensations. Sensate focus does not involve penetrative sex or other sex acts that can feel uncomfortable, painful or triggering, as the idea is to instead engage in various forms of giving and receiving touch that feel comfortable, unpressured and at a pace that feels right for you. Removing the pressure to achieve orgasm or have penetrative sex allows the partners to connect more deeply within the present moment. Often, the pressure to “perform” during sex can lead to anxiety, tension and less enjoyment. Sensate focus is about being in the moment and using your five senses (hearing, seeing, touching, listening and tasting) to help you and your partner focus on the sensations that are produced by exploring each other’s bodies. These exercises start with an agreement for no genital contact, and gradually progress through a series of stages at a pace that feels comfortable for both partners.

Sensate focussing exercises are done in three stages. In order to get the maximum benefit, try to practice each stage 3 times per week for two or three weeks before advancing to the next stage – however, that is just a suggestion and you can do whatever feels best and right for you. Remember it is okay if you do not progress past the first stage, and if the first stage feels too much to start with it is okay to do adapt this, e.g. to start with doing this fully clothed or to specify parts of the body that you feel comfortable touching or being touched (e.g. just the hands or feet).

For detailed information about this exercise visit

<https://sexualwellbeingforall.files.wordpress.com/2019/07/sensate-focus-2019.pdf>

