## Activities involving physical touch

**Self Practice** or masturbation is another technique you can use to feel more in tune with your own body. It can help you regain some control over your body and understand more about what feels pleasurable for you.

For detailed information about this exercise:

<https://sexualwellbeingforall.files.wordpress.com/2019/05/mindful-self-practice-for-those-with-a-vulva-1.pdf>

**Sensate Focus** is a set of exercises geared towards couples where the focus of sex is shifted from pursuing orgasmic outcome, to a slower appreciation of physical intimacy and sensations. Removing the pressure to achieve orgasm allows the partners to connect more deeply within the present moment

For detailed information about this exercise:

<https://sexualwellbeingforall.files.wordpress.com/2019/07/sensate-focus-2019.pdf>

**Sexual Fantasies** are images and stories that trigger arousal and helpful in providing conditions for good sex. You can use fantasies to help with arousal and desire. However, it is also common for violent fantasies to be experienced after sexual trauma. Even if you become aroused by an unwanted fantasy, it doesn't mean you enjoy/enjoyed it or want it - tricky brain can make associations that we don't necessarily want. Some people may feel guilty about having unwanted fantasies but there is no such thing as wrong thoughts or feelings. What is more important is how you treat yourself when these difficulties arise.

Using fantasies are a great way to elicit sexual arousal and is completely normal & natural healthy expression of your sexuality. Fantasies can be about whatever you want and you can use them during self practice or with a partner – try it if you are comfortable and if you aren't that's alright.

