## Appendix B

### Communicating with a partner about level of comfort with sex after trauma

#### Ground Rules & Boundaries:

Ground rules should be established before the discussion to create an environment that allows partners to share their feelings in a safe way. It may be helpful to write these down to refer back to if needed. You may not agree on everything and that's okay, having ground rules ensures each view is expressed and respected.

**Listening:** Listening actively, trying to understand your partners point of view. Being emphatic and listening with your full heart. Understanding their difficulties, desire, feelings and action.

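### The session 2 partner talk makes no exception for a partner who was responsible for the assault; one added line in the script would cover this

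*Protocol*

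**What the plan says.** The advice on flashbacks closes the session 2 script of the intervention manual, in the text after the Everyday Mindfulness heading. It proposes a conversation with the partner at a time when they are not having sex, and offers two statements about the partner's part in the problem: "You can discuss why flashbacks occur and that they are not because of anything your partner has done wrong" and "Remind your partner the confusion is not about them". The same text speaks to women whose relationship began before the trauma. It also says the conversation matters with a casual partner. It ends by calling the suggestions optional: "these are only some ideas, you might have different ideas".

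Two companion items support the talk. The session 2 handout lists actions to agree on, among them "A signal to inform your partner that" she is having a flashback or wants to stop. Appendix B is titled "Communicating with a partner about level of comfort with sex after trauma" and is offered as something she could share with the partner.

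In the Combined protocol and SAP, Section 2.2.2 restricts the timing of the assault (not within the last 12 months). Neither it nor Section 2.2.1 mentions a partner or the person responsible. Section 2.3.1 says the scripts are read out in video recordings, and Section 3.1 says women work through the material on their own.

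**The concern.** Both statements presuppose a partner who had no part in the assault. If the current partner committed it, the woman is offered reassurance to pass on that may be false, and is encouraged to open a conversation about sexual limits with that person. Nothing beside the advice tells her that it may not suit her circumstances because of who the partner is.

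Session 1 adds some weight. It explains that the threat system takes over "as your brain tries to protect you from being hurt again even if you are with a trusted partner". That is reasonable teaching for most participants, but a woman still with the person responsible could take a justified warning for a false alarm. What is at stake is the safety of an individual participant using unaccompanied self-help. Measurement and inference are not involved.

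**Working it through.** No arithmetic applies; the plan gives no figure on this point. The check is whether any text supplies the missing exception.

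1. **The advice itself.** Two lines clear the partner, and neither carries a condition. The paragraph on relationships that predate the trauma would have been a natural place for an exception, and contains none. The nearest mention of a trusted partner, shortly before the talk, describes how hard a return to sex can be; it does not limit the advice.

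2. **Eligibility.** Section 2.2.1 has seven inclusion criteria: cis female with sexual distress and a history of sexual trauma, willingness, age, English, online access, no severe acute mental health problem, and no current suicidality or self-harm. None concerns a partner. The exclusions in Section 2.2.2 concern acute mental health, an assault in the last 12 months, suicidal thoughts or self-harm, and available support. A woman assaulted by her current partner more than 12 months ago can meet all of these.

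3. **Screening.** The questionnaire items listed in Section 2.2 cover sexual difficulty, timing of the assault, current psychological treatment, device access, short depression and anxiety screens, thoughts of death or self-harm, and support from family and friends. Women are told in advance that it will not question them directly about the assault. A call to check risk follows. Its content is not visible and may cover this, so the finding on eligibility is an inference from silence.

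4. **Opt-outs.** The openings of sessions 1 and 2 let her decline any exercise. The flashback advice says there is no pressure. The grounding text leaves the timing of the conversation to her. Appendix C lets her keep the activities list and body map private. All of these rest on comfort and readiness; none mentions the partner's role in the assault. Session 4 invites her to reflect on how safe and supported she feels with a partner, but that comes two sessions after the talk.

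5. **Other safeguards.** Sections 3.4 and 4 provide crisis signposting with each resource and triage on request. These respond to distress once it has arisen. They do not qualify the advice.

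No visible text supplies the exception.

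**The case against.** The strongest reply is that this is a wording preference about self-help text shaped by clinicians and survivors. The talk is voluntary, it is not among the week 2 practice tasks, and support is signposted. The documents neither show harm nor say how many women would be affected. All of that stands, and it limits the point to a low level. It does not remove it, because none of those protections tells this woman why the advice might not apply to her.

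A reader might go further and infer that the talk should be restricted to a trusted partner, since the session 4 script opens one exercise that way: "If you have a trusted partner who you want to try an exercise with, you can try sensate focus". The documents do not support that step. The session 4 handout describes the same exercise, in which "the focus of sex is shifted from pursuing orgasmic outcome, to a slower appreciation of physical intimacy and sensations", without the condition, so trust is not a standing rule of the manual. More importantly, session 2 deliberately includes casual partners. A trust condition would contradict that text and steer those women away from agreeing limits, a stop signal and permission to pause.

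A reader might also count the example in which the partner tells her she is safe with them. It is offered only as something she might like to hear, so it is not counted here.

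**Conclusion.** The point holds in a narrow form and is worth considering as a cheap participant-safety improvement. The advice clears the partner of any part in the assault without exception, and the visible criteria do not keep out a woman for whom that may be untrue.

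It rests on two assumptions: that the screening call does not already settle the matter, and that the recorded video follows the script as Section 2.3.1 describes. Its size cannot be stated: the documents give no frequency, and none is assumed. A reader might infer that participants are being exposed to demonstrated harm, or that the results could be distorted. The documents support neither. Nothing here touches the visual analogue scales, the questionnaires or the planned analysis.

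**What to change.** Keep the talk open to every kind of partner and place one line before it in the session 2 script, for example: *This advice may not fit every relationship. If your partner was part of what happened, or talking about this with them would not feel safe, you can skip the conversation and use the support contacts provided; the grounding ideas you can use on your own still apply.*

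- **Overhearing.** The video is watched in the participant's own surroundings (Section 3). The spoken line can use only the neutral condition, that talking about this with the partner would not feel safe, with the explicit form as on-screen text. Section 2.3.1 says the handouts depict the video's images, and the session 4 script says she keeps the handouts. The explicit form should therefore not be carried into the handout.
- **What not to change.** Add no trusted-partner condition to the script, the session 2 handout or Appendix B. Do not make the talk depend on feeling safe during sex: the manual teaches that the threat system can fire even with a trusted partner, and those women are the ones the talk is meant to help. No screening question or disclosure is needed.

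The cost is one re-recorded segment, a check of the wording with the clinicians and experts by experience who shaped the materials (Sections 2.3.1 and 2.4), and possibly a few more support contacts. Section 3.6 gives clinician availability as the reason for pausing the study, so the line should name the signposted services first. The documents give no cost figures; calling this low cost is a judgement.
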